## **Power Analysis**

Size of study groups: 40; 80 total participants.

The necessary sample size was determined based on a review of past literature and power analysis. While no head-to-head studies of targeted approaches to ESI have been performed in the cervical spine, such studies have been conducted in the lumbar spine. Studies that used sample sizes of 20-30 participants per treatment group showed statistically significant differences ( $P < 0.05$ ). We will thus plan to recruit 100 participants (50 per group) in anticipation of a 20% attrition rate by 6-month follow-up, which would still result in approximately 40 participants per group, to allow for improved power to detect a difference between groups compared to the prior cited similar literature.

## **Procedures**

During the injection procedure, the participant will be positioned on a fluoroscopy table. Blood pressure and pulse oximetry monitors will be placed. A pre-procedure time-out will be performed, as is protocol in the University practice. Vital signs will be recorded immediately prior to and every 5 minutes during the injection procedure as is the current practice standard. Using fluoroscopic guidance, cervical ESI using one of the two approaches based on group randomization will be performed:

### *Transforaminal epidural steroid injection*

After injection of 1 to 2 mL of 1% lidocaine to the skin and subcutaneous tissues, a 25-gauge spinal needle will be placed at the level and side of radicular pathology, based on clinical

correlation of symptoms/signs and magnetic resonance imaging findings. Advancement to the appropriate target position in the neuroforamen will be performed under fluoroscopic guidance according to practice guidelines. Once a satisfactory target position is achieved and confirmed in both anterior-posterior and oblique views, 0.5 to 1 mL of contrast (Omnipaque-240; GE Healthcare, Princeton, New Jersey) will be injected under live fluoroscopic observation with or without digital subtraction angiography depending on suggestion of vascular uptake, as is standard practice and recommended by practice guidelines. Upon confirmation of a satisfactory epidural contrast pattern without vascular uptake, the injectate will be delivered: dexamethasone sodium phosphate 1mL (10mg/mL) and 0.5 ml of 1% preservative-free lidocaine (total volume 1.5 mL). After the injection procedure, participants will be observed and then discharged from the clinic with written discharge instructions (current standard practice).

#### *Catheter-targeted ESI via interlaminar access at the C7-T1 level*

After injection of 1 to 2 mL of 1% lidocaine to the skin and subcutaneous tissues, an 18-gauge 3.5-inch RX Epidural Needle (Epimed International Inc., Dallas, TX) will be placed at the C7-T1 level per practice guidelines and current safety recommendations, and a loss of resistance (saline) technique will be used to gain access to the epidural space; needle position will be confirmed in anteroposterior and lateral views. A radiopaque styled 21-gauge epidural catheter (C-KATH; Epimed International Inc., Dallas, TX) will be introduced through the Tuohy needle and advanced under live image guidance to the level and side of radicular pathology, based on clinical correlation of symptoms/signs and magnetic resonance imaging findings. Once a satisfactory target position is achieved with the catheter, 0.5 to 1 mL of contrast (Omnipaque-240; GE Healthcare, Princeton, New Jersey) will be injected. Upon confirmation of a satisfactory epidural contrast pattern, the injectate will be delivered: triamcinolone acetonide 1 mL (40mg/mL) and 0.5 ml 1% lidocaine (total volume 1.5 mL). After the injection procedure, participants will be observed for 20 to 30 minutes and then discharged from the clinic with written discharge instructions (current standard practice).

#### *Repeat injections*

If a repeat injection is required, the patient will remain in the study. We will perform the same injection to which the patient was randomized for the first injection. We will document how many injections are required for patients to report at least 75% improvement in neck and arm pain. No more than 2 repeat injections will be performed during the study. This protocol was used in a previous study.

#### **Data Collection:**

An electronic data collection sheet (via iPad) will be used to record all pre-procedure data (see data collection sheet):

- 1) Age (years).
- 2) Sex.
- 3) Height (cm).
- 4) Weight (Kg).
- 5) Duration of pain (weeks).

- 6) Location of cervical radicular pain based on clinical diagnosis: C2, C3, C4, C5, C6.
- 7) Radiologic diagnosis based on MRI of the Cervical Spine.

Before an initial injection, the following measures will be obtained:

- 7) NRS for pain; separate scores for neck pain and for arm pain
- 8) Neck Disability Index (NDI-5)
- 9) Medication Quantification Scale (MQS III) score
- 10) Daily opioid use in morphine equivalents

Immediately after injection the following will be obtained:

- 11) Fluoroscopy time
- 12) Post-injection NRS pain score; separate scores for neck pain and for arm pain
- 13) Adverse events, if they occurred

At intervals of 2 weeks, 1 month, 3 months, 6 months, and 1 year after injection, outcome measurements will be repeated. The Patient Global Impression of Change (PGIC) and a patient satisfaction score (five-point Likert scale: 1, very dissatisfied; 2, dissatisfied; 3, neither satisfied nor dissatisfied; 4, satisfied; and 5, very satisfied) will also be recorded. A single researcher blinded to group assignment collected all follow-up assessments in person, by e-mail, by telephone, or by mailed questionnaire.

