### **Risks/Benefits:**

Risks of study participation are the same as those for any standard fluoroscopically guided cervical ESI frequently performed in the PM&R Spine Clinic. These include: local infection, epidural hematoma or abscess, dural puncture and potential post-dural puncture headache, paresthesia during needle placement, pain at the injection side, failure of technique, allergy to latex or medications being used. Utilizing fluoroscopy, the risk of nerve damage, spinal cord injury or intravascular injection is less than 1:500,000. The length of stay and length of recovery is no longer than that of a standard ESI performed in the PM&R Spine Clinic at present.

There are no direct benefits to the individual by participating in this study. The patients will be presented with the same options of treatment whether they enroll in the study or decide not to. The information extracted from this study may provide the investigators a better understanding of patient's pain response following a cervical epidural steroid injection.

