### **Study Termination Criteria**

- Adverse events considered/identified by the medical staff during the procedure process
- The subject requests to be withdrawn from the study during the procedure.

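### Outcome visits are timed from the injection, so a randomised participant whose procedure is not completed has no defined follow-up, leaving the technique comparison open to post-randomisation selection

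*Combined protocol and SAP*

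**What the plan says.** All references are to the combined protocol and SAP.

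- **Allocation.** Subjects and Study design randomise patients to one of two techniques: transforaminal (Group 1) or catheter-targeted through C7-T1 (Group 2).
- **Time zero.** Data Collection gives one anchor for follow-up: "At intervals of 2 weeks, 1 month, 3 months, 6 months, and 1 year after injection, outcome measurements will be repeated". The 1-month primary assessment is one of these visits.
- **Delivery, Group 1.** The needle must first be in place ("Once a satisfactory target position is achieved and confirmed in both anterior-posterior and oblique views"). Then: "Upon confirmation of a satisfactory epidural contrast pattern without vascular uptake, the injectate will be delivered".
- **Delivery, Group 2.** The catheter must first be in place ("Once a satisfactory target position is achieved with the catheter, 0.5 to 1 mL of contrast" is then injected). Then: "Upon confirmation of a satisfactory epidural contrast pattern, the injectate will be delivered".
- **Non-completion.** Risks/Benefits includes "failure of technique" among the risks, with no rate. Study Termination Criteria lists "Adverse events considered/identified by the medical staff during the procedure process", and also a participant's request during the procedure to be withdrawn. It does not say whether outcome follow-up continues after either.
- **Retention.** Repeat injections keeps a patient who needs a further injection in the study, on the allocated technique. It does not cover a first procedure that could not be completed.
- **Analysis.** Data Analysis Plan defines the primary outcome as a proportion of participants, without saying whether that means randomised or injected. Statistical analysis names the tests but no analysis population and no rule for missing outcomes.

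**The concern.** The unit of randomisation is a technique, but the follow-up clock starts at an event that comes later and may not happen. If no injectate is given, a literal reader of Data Collection has no date from which to count one month. The primary outcome may then never be collected, and an analyst cannot recover it later. This makes the gap more than a missing analysis-set label.

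The Introduction presents the trial as evidence on which technique to recommend. Whether a technique can be completed is part of that answer. If non-completers drop out unrecorded, the comparison is between people selected after randomisation by how the procedure went. Randomisation no longer protects that comparison. With no rule written down, the denominator could also be settled after the results are known.

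**Working it through.** **1. The plan's own figure.** Power Analysis wants 40 per group and allows 20% attrition by 6 months: 40/(1 − 0.20) = 50 per group, 100 in total. This reproduces the recruitment target. The allowance is described as attrition by 6 months and does not mention procedures that are not completed. The 40 per group rests on the sizes of cited lumbar studies. No effect size, response rate or power is stated, so no loss of power can be set against a target.

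**2. What happens to a non-completer under the text.**

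| Step | Where stated | Result if no injectate is given |
|---|---|---|
| Baseline pain score | Data Collection, before the initial injection | Should be available |
| Visit dates | Data Collection, counted from the injection | Not defined on a literal reading |
| Staying in the study | Repeat injections; Study Termination Criteria | Not addressed; a procedural adverse event may end participation |
| Place in the primary proportion | Data Analysis Plan; Statistical analysis | Not stated |

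**3. Possible size.** The documents give no failure rate and no expected response rate, so all inputs here are assumptions. For one arm let *f* be the share not completed, *p* the response among those injected, and *q* the response among those not completed.

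- All-randomised response = p(1 − f) + q·f
- Response if only injected participants are counted = p
- Overstatement of that arm = p − [p(1 − f) + q·f] = f(p − q)

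With p = 50% and failures in one arm only:

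| f | All-randomised, q = 0 | Overstatement | All-randomised, q = 20% | Overstatement |
|---|---|---|---|---|
| 5% | 47.5% | 2.5 points | 48.5% | 1.5 points |
| 10% | 45.0% | 5.0 points | 47.0% | 3.0 points |
| 15% | 42.5% | 7.5 points | 45.5% | 4.5 points |

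At p = 60% and q = 0, 10% against 0% failure gives 0.10 × 0.60 = 6.0 points. At 50 per group, 10% is five people, which leaves 45 with an injection to start the clock.

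**4. When it vanishes.** The error in the between-arm difference is f₁(p₁ − q₁) − f₂(p₂ − q₂). It is zero if nobody fails, if failures respond as often as injected participants (q = p), or if f, p and q are the same in both arms. It changes sign with the arm that fails more: at p = 60% and q = 0, 10% failure in Group 2 alone gives the same 6.0 points the other way.

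**The case against.** **The documents exclude nobody.** This stands. A reader might infer that the plan computes the primary proportion among completed injections and that the comparison is therefore biased. No section says so. The text is silent, and bias follows only if failures occur, are left out, and differ between arms in frequency or prognosis. What the documents show is exposure to bias.

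**Injection may mean the whole session.** The Procedures section uses the term injection procedure for the full visit. Data Collection also records fluoroscopy time and adverse events immediately after injection, and both could exist for an abandoned attempt. On that reading the clock starts at the procedure. This is plausible, but it is not written. It gives no date to someone never attempted, and it does not settle the effect of the termination criteria or the analysis population.

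**The arms are not clearly unequal.** A reader might infer from the vascular-uptake phrase, stated only for Group 1, that Group 1 will lose more participants. The documents do not support that. Both arms have a position condition and a contrast condition, and a satisfactory pattern in Group 2 may already imply no uptake. Different procedures may well differ in completion, but the text cannot say which way.

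**Crossover.** A reader might also suppose that a failed participant would be given the other technique. Nothing provides for it, and Repeat injections keeps patients on their allocated technique.

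**The effect is small beside sampling error.** At 40 per group and 50% response the standard error of the difference is √(2 × 0.5 × 0.5/40) = 0.112, about 11 points, which is more than the illustrated 1.5 to 7.5. That is correct. However, a systematic shift does not average out, and this one is cheap to prevent.

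**Scoring every failure as a non-responder has its own error.** This also stands. If 20% of failures respond, that rule understates the arm by f × 0.20, or 1.0 to 3.0 points for f of 5 to 15%. It belongs in a sensitivity analysis.

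**Conclusion.** The point holds as a gap in the plan. Follow-up is anchored to an event that a randomised participant may not reach, the plan itself lists technique failure and procedural termination, and no section says how such a participant is followed or counted. The primary comparison is open to post-randomisation selection.

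The consequence for this trial cannot be sized or signed from the documents. The 2.5 to 7.5 points (no failures respond) and 1.5 to 4.5 points (20% respond) rest on three assumptions: 5 to 15% failure in one arm, none in the other, and 50% response among those injected. The documents do not support saying that the comparison is biased, or that either arm is favoured.

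The change should be made, because outcomes that are not collected cannot be restored at analysis.

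**What to change.** **Data Collection.** Time all visits from the date of the first attempted study procedure, or from randomisation if none is attempted. Collect outcomes on every randomised participant, whether or not injectate was delivered, unless consent to follow-up is withdrawn.

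**Study Termination Criteria.** State that stopping the procedure does not by itself end outcome follow-up.

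**Data Analysis Plan.** Compute the primary proportion in all randomised participants by assigned group, using observed 1-month outcomes. Add a sensitivity analysis that counts undelivered injections as non-responders. Report the completion of each technique by arm.

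The cost is a few sentences in three sections and a few extra contacts for the existing blinded assessor. The responder rate may be slightly lower in the arm with more failures. How a failed procedure is managed clinically is for the sponsor and investigators; no rule is proposed here.

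### After a repeat injection the plan guarantees no dated follow-up contact, and no follow-up contact after any injection is said to ask about adverse events

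*Combined protocol and SAP*

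**What the plan says.** The combined protocol and SAP deals with this in several places.

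- *Repeat injections*: "If a repeat injection is required, the patient will remain in the study". The procedure is unchanged: "We will perform the same injection to which the patient was randomized for the first injection". The only limit is on number: "No more than 2 repeat injections will be performed during the study". No earliest time, latest time or minimum interval is given.
- *Data Collection*, baseline: "Before an initial injection, the following measures will be obtained".
- *Data Collection*, at the procedure: "Immediately after injection the following will be obtained", followed by fluoroscopy time, NRS and adverse events. This is the only place in that section where adverse events are named.
- *Data Collection*, follow-up: "At intervals of 2 weeks, 1 month, 3 months, 6 months, and 1 year after injection, outcome measurements will be repeated", with PGIC and satisfaction added. One blinded researcher makes these contacts in person, by e-mail, by telephone or by post.
- *Risks/Benefits*: "These include: local infection, epidural hematoma or abscess, dural puncture and potential post-dural puncture headache", among others. The risks are attached to the procedure and do not distinguish a first injection from a repeat.
- *Safety Monitoring Plan*: the team undertakes to keep in close touch with participants, without dates. Adverse reactions are to be reviewed whenever study drug is given and whenever a sample is taken, but the protocol describes no samples.
- *Exclusion criteria*, item 1, treats the study as lasting 6 months, and *Power Analysis* counts attrition to 6 months. *Data Collection* follows participants to 1 year.

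**The concern.** A repeat is the same procedure with the same listed risks, yet the schedule speaks of a single, unqualified injection. If visits are counted from the first injection, that injection is followed by a contact at 14 days, while a repeat is followed by whichever visit happens to come next. If the clock restarts instead, each repeat gets its own 2-week contact, but outcome visits stop lining up across participants. With no minimum interval, a repeat before 1 month would then move the primary assessment or leave two candidate 1-month visits.

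Two things are at stake. A complication that appears after the participant has gone home could be recorded late, or not at all, because no dated contact is assigned to find it. And the time origin of every outcome visit, including the primary one, is open for anyone who is re-injected.

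**Working it through.** The plan gives no figure for the wait between a repeat and the next contact, so there is nothing to reproduce. The check takes differences between consecutive scheduled contacts.

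**Inputs.** Contact times are from *Data Collection*: 2 weeks, then 1, 3, 6 and 12 months. With 365.25 / 12 = 30.44 days per month, these fall at about days 14, 30.4, 91.3, 182.6 and 365.25. The maximum of two repeats is from *Repeat injections*, and the 100 participants are from *Subjects* and *Power Analysis*.

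**Reading A: one clock from the first injection.** The longest wait for a repeat given just after visit *k* is time(*k*+1) − time(*k*).

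| Repeat given just after | Next dated contact | Wait |
|---|---|---|
| 2-week visit | 1 month | 30.4 − 14 = about 16 days |
| 1-month visit | 3 months | 91.3 − 30.4 = about 61 days |
| 3-month visit | 6 months | 182.6 − 91.3 = about 91 days |
| 6-month visit | 1 year | 365.25 − 182.6 = about 183 days |

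The comparison is 14 days after the first injection. If the study ends at 6 months, the last row disappears and the longest wait between contacts is about 91 days. If it runs to 1 year, the longest is about 183 days. These are worst cases: a repeat given shortly before a visit waits less.

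**Reading B: the clock restarts at each injection.** The first contact is 14 days after every injection. The gap closes, at the price of the misaligned outcome visits described above.

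**Which reading?** Three features favour A: the word for the injection is singular, baseline is tied to the initial injection, and the primary outcome in *Data Analysis Plan* sits at one 1-month assessment. None of them states the rule.

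**What the contacts collect.** Under either reading, the follow-up contacts repeat outcome measurements and add PGIC and satisfaction. Adverse events are not named at any of them.

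**Ceiling on repeats.** 100 participants × 2 repeats = 200, out of 100 × 3 = 300 possible injections. The documents give no expected repeat rate.

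**The case against.** The strongest reply is that the plan already provides several safeguards.

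- The immediate items are introduced without the word initial, unlike the baseline items, so they read naturally as covering every injection. This stands: recording at the time of a repeat is not missing.
- The *Safety Monitoring Plan* promises contact throughout and a review at each drug administration, and a repeat is one. This also stands, but the promise carries no dates, and review at administration comes before a participant goes home. A second repeat would be a review point after the first, but a last repeat has none.
- The procedure sections provide observation and written instructions at discharge. These help the participant, but they do not set a time at which the study asks.
- The 6-month wait is an extreme. It needs a repeat just after the 6-month visit and follow-up to 1 year. This is right, and so the figure is given as conditional.

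A reader might also infer more than the documents support.

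- *Harm is looked for at 2 weeks after the first injection but not after repeats.* The text does not say so. Adverse events are not named at the 2-week contact after any injection. The difference under reading A is in contact, not in a stated adverse-event question.
- *The safety comparison between arms is biased.* *Data Analysis Plan* lists no safety endpoint, *Statistical analysis* specifies no adverse-event comparison, and nothing documents a difference in repeat rates between arms.
- *The schedule is fixed to the first injection.* That is the likelier reading, but it remains an inference.

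**Conclusion.** The point holds in a limited form. The plan leaves the time origin of follow-up unstated for re-injected participants and assigns no dated contact to capture delayed adverse events after a repeat, unless the clock restarts. Even where contacts are dated, including those after the first injection, adverse events are not among the items named.

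On a single clock, the worst-case wait after a repeat is about 2 to 3 months within a 6-month study and about 6 months if follow-up runs to 1 year. This rests on first-injection timing, on a repeat falling just after a visit, and on which study duration applies. It also assumes that some of the listed risks, such as infection, can become apparent after discharge; *Risks/Benefits* gives no timing.

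This is a cheap improvement to safety recording. It is not evidence of bias in the comparison of arms.

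**What to change.** 1. In *Repeat injections* and *Data Collection*, state that outcome visits are timed from the first injection.
2. Reconcile the 6-month duration in *Exclusion criteria* with the 1-year contact in *Data Collection*.
3. Add an adverse-event question to every existing follow-up contact.
4. Add one brief adverse-event contact, by telephone or e-mail, 2 weeks after each repeat injection, unless a scheduled contact already falls near that date.
5. Report adverse events by arm, per participant and per injection.

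The cost is a protocol amendment and at most 200 short contacts. That number is a ceiling, reached only if all 100 participants receive both repeats and no visit falls near the 2-week date. The interval, modes of contact and staff are already in the plan. No dose, procedure or rule for repeating an injection changes.
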